11.1 OVERVIEW

The ACCESS distributed data management system was designed and implemented by the Clinical Coordinating Center staff. The system allows Clinical Center staff to enter data from case and control study forms and to transmit the data to the Clinical Coordinating Center. The system provides other functions including an inventory of all forms entered. Clinical Center staff have responsibility for maintaining the integrity of the local database by performing regular backups. The Clinical Center staff are responsible for the security of the distributed data management system hardware.

Clinical Center staff use an automated telephone response system (ATRS) to register cases. This system is also used to monitor the Clinical Center progress in the enrollment of potential controls identified by random digit dialing (RDD).

A manual (ACCESS Procedures Manual, Volume III) describing the procedures for using the ACCESS data management system was provided by the Clinical Coordinating Center to each Clinical Center.

11.2 DATA ENTRY

The data entry function provided uses screen images of forms. Data are edited for valid codes and ranges during data entry. A local edit, which includes a check of consistency of data within the form, is performed after data entry. Messages are printed locally. A more extensive edit is performed after the data are transmitted to the Clinical Coordinating Center. Clinical Center staff are able to correct items using a screen image of the data form. A record of each change is stored in the database. As forms are entered or corrected, they are marked for transmission to the Clinical Coordinating Center.

Each staff member certified by the Clinical Coordinating Center to perform data entry is assigned a data entry certification number. Paper copies of a sample of forms are requested by the Clinical Coordinating Center at regular intervals to assess the quality of data entry.

11.3 DATA TRANSMISSION

Data are transmitted to the Clinical Coordinating Center on a regular schedule. Once every week, Clinical Coordinating Center staff link with the computer at each Clinical Center for transmission of data entered in the previous week. At that time, Clinical Coordinating Center staff may also transmit study reports or new software for use in the Clinical Center.

11.4 OTHER FUNCTIONS

Screening logs for cases and potential controls identified by the RDD Interview Group to match enrolled cases include a limited amount of information (see Section 6.2) concerning each potential case and control identified. Completion of screening logs for cases was discontinued in October 1997. These logs are entered and updated locally using the distributed data management system.

Data entry certification is completed by entering a standard set of forms into the local database. These data are sent to the Clinical Coordinating center during regularly scheduled transmissions.

Local reports include case appointment schedules for cases enrolled in the Clinical Course Study, visits expected in a calendar month for these cases, delinquent forms for cases and controls, and calculation of reference dates for controls (implemented July, 1997).

Software to assist in scheduling case and control appointments is also available.

11.5 DATABASE BACKUP

The Clinical Coordinating Center database is the archive for all data from the Clinical Centers. Each individual Clinical Center must protect its own computer system from loss of study data. Software is provided for backup of the database as well as for backup of the

system. The ACCESS database is backed up after each data entry session. The system is backed up at regular intervals. A recommended procedure for system backup is to copy all files once each week and to copy only changed files daily.

11.6 REQUIREMENTS

The hardware for the distributed data management system requires a secure workspace with a power source (preferably protected from surges and interruptions) and a dedicated telephone line. Space to store paper and labels should be available. A touch-tone phone is required to use the automated telephone response system (ATRS).

11.7 CASE AND CONTROL REGISTRATION

Cases are registered using an automated telephone response system (ATRS). Clinical Center staff complete a worksheet with identifying information and eligibility information. Clinical Center staff call the ATRS and enter the worksheet data using a touch-tone telephone. Using the case registration data, potential controls are identified through random digit dialing. After the potential control has been contacted, Clinical Center staff update the potential control's status in ACCESS using the ATRS.

11.8 ELECTRONIC DOCUMENTS (IMPLEMENTED MAY 1998)

The ACCESS Protocol and Procedures Manuals are available in electronic form on ACCESS microcomputers. Revised documents are downloaded during data transmission (Section 11.3).

CHAPTER 12

STATISTICAL CONSIDERATIONS

12.1 INTRODUCTION

Data analyses will be carried out for two main purposes. One is to monitor the performance of the Clinical Centers with respect to recruitment of cases and controls, follow-up of cases, adherence to the study protocol, and accuracy and completeness of study data. The second main purpose for data analyses is to seek answers to the study research questions and objectives. These analyses will involve the application of case control and longitudinal data analysis methods. Interim research data reports will be generated every six months and presented to the Data and Safety Monitoring Board. A final report will be generated at the termination of recruitment and followup of the cases.

The analyses proposed for A Case Control Etiologic Study of Sarcoidosis (ACCESS) are robust from the point of view that they will allow for multivariate analyses, missing data and different lengths of follow-up of the cases.

There are two types of analyses in ACCESS. First, a case control study will be conducted with one matched control for each case (case control pairs). Second, the first 240 cases enrolled in ACCESS will be followed for two years.

For the case control study, controls will be matched to cases on the basis of age (± 5 years), gender and race: the control will be identified using random digit dialing methods. The final statistical design of the case control study will have adequate control mechanisms for bias and confounding and the design will allow for the detection of important associations. Most important will be the rigid matching of race in the paired design. Among the hypotheses being tested are the effect of modifications of certain exposures among patients with a genetic predisposition for sarcoidosis. Certain alleles are not common to both black and white comparisons. Therefore, it will be important to match for race in these analyses. Evaluations of the adequacy of the number

of cases and controls and of the power of the major proposed comparisons are important aspects of establishing if meaningful associations of exposure variables with cases can be measured.

Assessments of the number of cases in the longitudinal analysis must take account of the different types of outcome data that will be collected, as well as the data collection techniques for independent and dependent variables.

Five categories of sarcoidosis cases will be recruited, and progression or regression of the disease may be different according to the different categories. Therefore, it is anticipated that subgroup analyses will be part of ACCESS.

In the clinical course study, synthetic case control methods will be used to analyze data obtained from specimens stored in the Central Repository. This design will produce a substantial cost savings over the standard designs that require routine analyses for all samples collected, and has the added advantage that certain assays may not be developed at this time, but could be performed later on banked specimens.

12.2 POWER CALCULATIONS

12.2.1 Power Calculations for the Case Control Study

Determination of power for matched pair designs have been developed by Miettinen (Miettinen, 1969) and Walter (Walter, 1980) and more recently by Lubin, Gail, and Ershow (Lubin et al, 1988). These formulas can be used to evaluate the adequacy of the number of cases and controls in the case control design.

For binary exposure variables analyzed as part of the case control study the formula for power is the following:

power '
$$\ddot{O}\left(\frac{\ddot{a}@\hat{e}@N}{\sqrt{g @\hat{e}@(\hat{e}\%1) N/2}} \& Z_{\dot{a}}\right),$$

where $A_{\overline{k}}$ would be 1.96 ($\dot{a} = 0.05$ two sided test), N is the number of cases, \hat{e} is the number of controls matched to each case ($\hat{e} = 1$ in ACCESS), \ddot{a} is the difference between the expected percentages of cases and controls exposed to the risk factor of interest ($p_1 - p_0$) and \emptyset is the

proportion of case control pairs in which one person's exposure history differs from the other (discordance). Breslow and Day (Breslow and Day, 1980) have shown that only the discordant pairs in a case control study contribute information to the estimation of the odds ratio. Thus, discordant pairs are "informative".

Matched case control study analysis differs from prospective study or clinical trials data analysis. Psi (\emptyset) is dependent upon the degree of correlation between the probability that a case is exposed (has an attribute) and the probability that the control for this case is exposed. This correlation will be a function of the values of the matching covariates and thus the probabilities of exposure will vary from pair to pair and a correlation between these probabilities will be present.

Let p_1 be the expected percentage of exposure in the cases,

p₀ be the expected percentage of exposure in the control,

- and $Cov(p_1,p_0)$ be the expected covariance of the matched case and control exposure probabilities.
- then $\phi = p_1 + p_0 2 p_1 p_0 2 cov (p_1, p_0)$.

This can be rewritten to:

$$a' \frac{1\%\ddot{a}^2}{2} \& 2(p\&0.5)^2 \& 2cov (p_1, p_0)$$

with
$$\overline{p}' = \frac{p_1 \% p_0}{2}$$

Examination of this equation shows that \emptyset will generally be less than 0.55 except when \ddot{a} is very large, and/or the cov (p_1 , p_0) < 0. In general, matching produces positive correlations and it can be expected that there will be less than 55% of case control pairs that are informative.

Tables 1 and 2 show the power of the proposed design to detect specified odds ratios as a function of the correlation (0.5 and 0.0) between case and control exposure rates, and the expected value of the control exposure rate with the alpha level for the test set at 0.05 (two sided test) and with 720 cases. With the proposed number of cases and controls there will be 98.6% power to detect odds ratios of 0.7 or less and 98.8% power to detect odds ratios of 1.4 or greater when the correlation between case and control exposures is 0.5 (Table 1) and the proportion of controls exposed is 0.3. If the correlation between cases and control exposures is 0.0 (a conservative estimate), the power is reduced to 84.3% and 85.1%, respectively. If the proportion of controls exposed is reduced to 0.05 there is at least 90% power to detect an odds ratio of 2.0.

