6.3.1 Random Digit Dialing Controls

Cases are matched in a one to one ratio to controls selected through random digit dialing. Random digit dialing facilitates the selection of a control group that approximates a probability sample in the population. Random digit dialing (RDD) is used to identify potential controls through an unbiased clustered random sample of households with telephones (Waksberg, 1978). Cluster sampling of telephone households and a stratified sample of age-, gender-, and self-identified racematched individuals are used (Hartge et al, 1984).

The groups selected to generate telephone numbers, Survey Sampling Inc. (SSI), and to perform the telephone recruitment of potential controls, Telesurveys Research Associates (Random Digit Dialing (RDD) Interview Group), work under the direction of the Clinical Coordinating Center. The RDD callers are responsible for making initial telephone contact with potential controls in the geographic areas of the Clinical Centers.

Once the RDD Interview Group recruiter has established the eligibility, availability and willingness of the potential control to participate, the potential control is informed that an interviewer from the Clinical Center will be in touch soon to set up an appointment to meet for questionnaire

administration and phlebotomy. Potential controls are informed that a payment will be given to them after they complete the study interview to reimburse them for parking costs, meals and other expenses (including lost time from work) at the medical center, and transportation costs.

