12.2.3 Subgroup Analyses

As part of ACCESS, Clinical Center investigators may want to make comparisons of cases and controls within certain strata. For instance, there could be comparisons of female cases and controls, comparisons of black cases and controls, and comparisons of erythema nodosum cases with their matched controls. Each of these subgroup comparisons will bring with it a different number of cases and controls and power for making comparisons. Effect sizes that could be detected in one subgroup analysis, might not be detected in another analysis. Power analyses have been performed for statistical comparisons that will be performed in subgroups representing 7%, 14%, 25%, 50% and 75% of the entire case control study population. These percentages may be representative of comparisons for a small substudy (7% and 14%), within a sarcoidosis category (20%), within a gender comparison (50%), and within the black population (75%, published reports put the percentage of sarcoidosis cases who are black between 60% and 80% in some cities). Power calculations for binary exposure variables when performing analyses in subgroups are presented in Tables 3 through 12. There is a substantial change in the odds ratios that can be detected with adequate power depending upon the number of cases in the subgroup. For instance, fixing the odds ratio at 0.7, the correlation between case-control response at 0.5, and the proportion of controls exposed at 0.3, there is 54.8%, 83.7% and 95.0% power to detect this odds ratio for 180, 360 and 540 case control pairs, respectively.

As part of each subgroup analysis, a statistical test will be performed to determine if the findings relating to exposures in one subgroup correspond to the findings in the complimentary subgroup (an interaction test). For instance if a risk factor is discovered for females, is that risk

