12.3.2.2 Matched Case Control Designs

Cases and controls will be matched with respect to the case's age (± five years), gender, and race. Random digit dialing may implicitly match cases and controls for geographical location. A matched design will be most appropriate for analyzing the data in this study. Simple presentations of matched case control data should follow the methods outlined by Breslow and Day. Categorical data will be presented using a cross tabulation of the number of cases exposed versus the number of controls exposed. Standard chi-square analyses will not be performed on these tables. Instead, methods for estimating the odds ratio from McNemar's test will be used to estimate the measure of association. Since the proposed number of cases is large, it will be possible to estimate 95% confidence intervals using the binomial approximation. For continuous variables, presentation of means will be accomplished using a paired t-test. These analyses can be performed using Proc Means in SAS. This will have the effect of adjusting for the matching variables. A point estimate for the difference in case and control means will be obtained and a 95% confidence interval for the difference will be calculated using this procedure.

It will be important to adjust study results for confounding variables that could bias the results of the case control study. Analyses using one more exposure variable(s) will be performed using conditional logistic regression methods. This method can be used to estimate odds ratios for casecontrol studies.

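### The correlation-0.5 power tables are indexed, without saying so, on the marginal odds ratio, so they overstate power for the matched-pair odds ratio that the study will report; zero correlation is the favourable end of the expected range, not the conservative one

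*Protocol*

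**What the plan says.** Protocol section 12.2.1 sets "the alpha level for the test set at 0.05 (two sided test) and with 720 cases". Where "the proportion of controls exposed is 0.3" and the correlation is 0.5, it states "98.8% power to detect odds ratios of 1.4 or greater when the correlation between case and control exposures is 0.5". The companion figure on the protective side, for an odds ratio of 0.7, is given as 98.6%. It then adds: "If the correlation between cases and control exposures is 0.0 (a conservative estimate), the power is reduced to 84.3% and 85.1%, respectively". For a control exposure of 0.05 it claims 90% power or more at an odds ratio of 2.0. It does not say which odds ratio the tables use.

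The same section notes that only discordant pairs inform the odds ratio and that matching usually makes the exposure correlation positive. Section 12.3.2.2 rules out ordinary chi-square tests. The odds ratio from McNemar's test is to be "used to estimate the measure of association", with conditional logistic regression for adjusted analyses.

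Two further statements draw on the correlation-0.5 tables. For an odds ratio of 0.7, section 12.2.3 says "there is 54.8%, 83.7% and 95.0% power to detect this odds ratio for 180, 360 and 540 case control pairs". Section 1.5.1 claims 86% or more for 180 pairs, exposure 0.1 and odds ratio 2.0.

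**The concern.** In a matched design, two odds ratios can be written down. The marginal one compares overall exposure in cases and controls. The matched-pair one is the ratio of the two kinds of discordant pair, and it is what McNemar's method and conditional logistic regression estimate. They coincide when exposures within pairs are uncorrelated and separate as the correlation grows.

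The protocol's tables show power rising when the correlation goes from 0 to 0.5. That is the pattern for a fixed marginal odds ratio. For a fixed matched-pair odds ratio, positive correlation removes discordant pairs, and power should fall. If the tables index one quantity and the analysis reports the other, the headline and subgroup powers do not describe the reported odds ratio, and the correlation presented as cautious is the optimistic one.

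**Working it through.** **Inputs.** Two-sided alpha 0.05 (z = 1.96), N = 720 pairs and control exposure p0 = 0.3 are from 12.2.1. The 1:1 ratio is from 6.3.1 ("Cases are matched in a one to one ratio to controls selected through random digit dialing"). With one control per case, the power formula in 12.2.1 reduces to

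power = Φ( |δ|·√(N/ψ) − 1.96 ), with δ = p1 − p0 and ψ = p1 + p0 − 2·p1·p0 − 2·cov.

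**Step 1: reproduce the stated figures.** Take p1 from the marginal odds ratio, p1 = OR·p0/(1 − p0 + OR·p0), and cov = r·√(p1·q1·p0·q0), where q = 1 − p.

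- OR 1.4, r = 0.5: p1 = 0.42/1.12 = 0.375; cov = 0.5·√(0.375·0.625·0.3·0.7) = 0.1109; ψ = 0.375 + 0.3 − 0.225 − 0.2219 = 0.2281. Power = Φ(0.075·√(720/0.2281) − 1.96) = Φ(2.25) = 0.988.
- OR 0.7, r = 0.5: p1 = 0.21/0.91 = 0.2308; ψ = 0.1992; δ = −0.0692; power 0.986.
- r = 0: 0.851 and 0.843.

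All four agree with 12.2.1. A check of 30 cells across the six sample sizes agrees to about 0.001.

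**Step 2: find the matched-pair odds ratio in those rows.** The discordant-pair probabilities are b = (ψ + δ)/2 (case exposed only) and c = (ψ − δ)/2 (control exposed only). At p0 = 0.3 and r = 0.5:

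| Tabulated OR | b | c | b/c |
|---|---|---|---|
| 0.7 | 0.0650 | 0.1342 | 0.48 |
| 1.4 | 0.1516 | 0.0766 | 1.98 |
| 2.0 | 0.2089 | 0.0473 | 4.41 |
| 3.0 | 0.2801 | 0.0176 | 15.9 |
| 4.0 | 0.3316 | 0 | infinite |
| 5 | 0.3706 | −0.0113 | impossible |
| 20 | 0.5568 | −0.0387 | impossible |

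Two binary exposures with marginal odds ratio OR above 1 cannot have a correlation above 1/√OR. Read as marginal odds ratios, the rows above 4 in the correlation-0.5 tables therefore describe populations that cannot exist. At r = 0, b/c equals the tabulated odds ratio, so Tables 2, 4, 6, 8, 10 and 12 are right on either reading.

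**Step 3: hold the matched-pair odds ratio fixed.** Setting b/c = OR gives δ = ψ·(OR − 1)/(OR + 1). Solve this with the ψ formula for p1 at the stated p0 and r, then apply the same power formula.

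- OR 1.4, r = 0.5: p1 = 0.3363, ψ = 0.2180, δ = 0.0363; power = Φ(√(720·0.2180)·0.4/2.4 − 1.96) = Φ(0.128) = 0.551.
- OR 0.7, r = 0.5: p1 = 0.2641, ψ = 0.2036; power = Φ(√(720·0.2036)·0.3/1.7 − 1.96) = Φ(0.177) = 0.570.

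Simulating McNemar's test (400,000 replicates) gives 55.1% and 57.1%.

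| Setting | Stated | r = 0 | r = 0.2 | r = 0.5 |
|---|---|---|---|---|
| 720 pairs, p0 0.3, OR 1.4 | 98.8% at r = 0.5 | 85.1% | 76.0% | 55.1% |
| 720 pairs, p0 0.3, OR 0.7 | 98.6% at r = 0.5 | 84.3% | 76.2% | 57.0% |
| 180 pairs, p0 0.3, OR 0.7 | 54.8% at r = 0.5 | 31.7% | 26.7% | 18.6% |
| 360 pairs, p0 0.3, OR 0.7 | 83.7% at r = 0.5 | 55.5% | 47.2% | 32.7% |
| 540 pairs, p0 0.3, OR 0.7 | 95.0% at r = 0.5 | 72.9% | 63.9% | 45.6% |
| 180 pairs, p0 0.1, OR 2.0 | 86%, no r given | 60.1% | 48.6% | 30.6% |
| 720 pairs, p0 0.05, OR 2.0 | 90%, no r given | 90.9% | 81.2% | 56.8% |

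The last three columns are for the matched-pair odds ratio. The 86% in 1.5.1 matches the correlation-0.5 cell (Table 7, 0.862). The protocol's own Table 8 gives 0.601 for the same setting at zero correlation, so 86% is not a minimum on either reading of the odds ratio.

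**The case against.** The best defence is that nothing is miscalculated. Section 12.2.1 defines the alternative through p1 − p0 and the discordance, and McNemar's test works on exactly that contrast. If p1 is 0.375, p0 is 0.3 and the correlation is 0.5, the planned test does have 98.8% power. That stands: a reader might infer that 98.8% is an arithmetic error, and it is not. It answers a question about a different odds ratio from the one to be reported.

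Several main claims also do not depend on correlation 0.5. The zero-correlation powers are printed beside the others and tabulated for every sample size. The claim for odds ratio 2.0 at exposure 0.05 agrees with the zero-correlation cell (0.909, Table 2). The subgroup claim in 1.5.1 for odds ratio 3 at exposure 0.10 is met at zero correlation even with 180 pairs (0.957, Table 8). Section 12.4 quotes no correlation and no binary odds ratio, so it needs no restatement on this ground. All of this stands.

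The documents also give no expected correlation for any exposure. The value 0.5 is one of only two tabulated, so 55–57% is the result in the protocol's own headline scenario, not a forecast. At 0.1 the loss is modest (81.0% and 80.7%).

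Finally, zero correlation is not an absolute upper bound: at −0.1, power for a matched-pair odds ratio of 1.4 is 88.4%. The protocol allows for negative covariance but expects positive, so the conservative label still points the wrong way over the expected range.

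**Conclusion.** The point holds as a mismatch between the odds ratio that indexes Tables 1, 3, 5, 7, 9 and 11 and the one that the analysis estimates. At correlation 0.5 the stated powers exceed those for the reported odds ratio by 98.8 − 55.1 = 43.7 and 98.6 − 57.0 = 41.6 percentage points in the headline example. In the subgroup example the excess is 36.2, 51.0 and 49.4 points for 180, 360 and 540 pairs. The 86% in 1.5.1 is too high by about 26 points even at zero correlation.

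This rests on two readings: that the odds ratio of interest is the one from McNemar's method and conditional logistic regression, as 12.3.2.2 says, and that 0.5 is the correlation of the paired exposures, which is how the tables use it.

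A reader might infer that 720 pairs are too few. The documents do not support that: at matched-pair odds ratios of 1.4 and 0.7 and control exposure 0.3, power is about 84–85% when the correlation is near zero, and how far it falls depends on correlations that the documents do not give.

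**What to change.** - State in 12.2.1 which odds ratio the tables use.
- Re-index Tables 1, 3, 5, 7, 9 and 11 on the matched-pair odds ratio, solving for p1 as in step 3. No row need be deleted: the rows above 4 are impossible only as marginal odds ratios. For example, a matched-pair odds ratio of 5 at p0 = 0.3 and r = 0.5 has b = 0.217 and c = 0.043.
- Remove the conservative label from zero correlation and describe it as the most favourable of the non-negative correlations.
- Restate the powers quoted in 12.2.1 and 12.2.3 and the 86% in 1.5.1, for example at correlations 0, 0.2 and 0.5, with the correlation given beside each figure.

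The cost is a recalculation, replaced tables and a few sentences, with less favourable stated powers. The zero-correlation tables, the number of pairs, recruitment and the analysis methods do not change.
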